7.7. Safety Analysis

7.7.1. Adverse Events

- Reported adverse events will be reclassified using MedDRA version 20.1.
- Events newly occurring following the administration of the investigational product and events that have worsened compared to their status prior to treatment initiation will be tabulated as treatment-emergent adverse events (TEAEs).
- SOCs will be tabulated and displayed in the internationally recognized order, and PTs will be tabulated and displayed in descending order of the number of subjects with said events in the active drug group, in descending order of the number of subjects with said events in the placebo group,

and in PT code ascending order.

- When counting the number of subjects with a particular event by PT, if the same subject experienced a different PT adverse event, then this subject will be counted once for each PT. If the same subject experiences the same PT adverse event multiple times, then this subject will be counted only one time for this PT.
- When counting the number of subjects with a particular event by SOC, if the same subject experienced a different SOC adverse event, then this subject will be counted once for each SOC. If the same subject experiences the same SOC adverse event multiple times, then this subject will be counted only one time for this SOC.
- When tabulating events by severity (severe, moderate, mild), subjects will be counted as described below.
 - (1) If the same subject experiences adverse events at different levels of severity, then this subject will be counted once, at the highest level of severity.
 - (2) If the same subject experiences multiple adverse events at the same level of severity, then this subject will be counted once, at this level of severity.
 - (3) If the same subject experiences the same adverse event multiple times, this subject will be counted once at the highest level of severity.
- Calculation of the incidence per 1000 person-years

Safety Endpoints

Adverse events, adverse reactions, serious adverse events, serious adverse reactions, adverse events leading to study treatment discontinuation, adverse reactions leading to study treatment discontinuation, adverse events leading to death, adverse reactions leading to death, hypoglycemia, severe hypoglycemia, documented symptomatic hypoglycemia, asymptomatic hypoglycemia, probable symptomatic hypoglycemia, relative hypoglycemia, the adverse events in the PT list for hypoglycemia in the attachment, lower limb amputation, volume depletion, fracture, osmotic diuresis, renal-related adverse events, diabetic ketoacidosis, acute pancreatitis, urinary tract infection, upper urinary tract infection, female mycotic genital infection, male mycotic genital infection, hypoglycemia, malignancy

N: Safety endpoint sample size

P: Sum total of the assessment period (in years) of the incidence per 1000 person-years for each subject in the safety analysis population

Incidence per 1000 person-years = $N/P \times 1000$ (1000 subject-years)

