4.12. Adverse Drug Reaction

Adverse events for which it has been determined that there is a “reasonable possibility” of there being a causal relationship to the investigational product will be handled as adverse reactions.

4.13. Period of Assessment of the Incidence Per 1000 Person-Years of Each Safety Endpoint

1. Subjects for whom the date of the visit at Week 4 of the follow-up observation period can be obtained

Period of assessment of the incidence per 1000 person-years (in years) = (Day of the visit at Week 4 of the follow-up observation period – First day of the treatment period + 1)/365.25

2. Subjects for whom the date of the visit at Week 4 of the follow-up observation period can not be obtained

Period of assessment of the incidence per 1000 person-years (in years) = (Final assessment time point^{*1} – First day of the treatment period + 1)/365.25

^{*1}Final assessment time point

If the day of discontinuation can be obtained: Day of discontinuation

If the day of discontinuation cannot be obtained: Day of the final scheduled visit^{*2}

^{*2}Day of the final scheduled visit

The latest date will be used, regardless of the allowable time window

5. Analysis Sets

The analysis of efficacy is performed in the full analysis set (FAS). In addition, a secondary analysis of the primary endpoint will be performed in the per-protocol set (PPS), as well. Safety analysis is performed in the safety analysis set. The data sets analyzed are defined below. The study sponsor finalizes the details of how the subjects are handled by the time of the database lock.

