5.2. Safety Analysis Sets

The analysis sets consisting of all randomized subjects other than the following constitute the safety analysis sets.

- All subjects who did not take the investigational product at all
- All subjects for which no post-randomization safety data are available

6. Handling of Data

The data handling procedures are described below, except for issues that are determined by the study sponsor's case review board.

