7.7.3. Adverse Events of Special Interest

Analysis population(s): Safety analysis set

Analysis parameter(s): Lower limb amputation, volume depletion, fracture, osmotic diuresis, renal-related adverse events, diabetic ketoacidosis, acute pancreatitis, urinary tract infection, upper

urinary tract infection, female mycotic genital infection, male mycotic genital infection, hypoglycemia, and malignancies

Analysis method:

For adverse events of special interest occurring in the adverse event tabulation period, the numbers and proportions of subjects experiencing said events, as well as the incidence per 1000 person-years, will be presented for each treatment group.

The number and proportion of subjects experiencing the event, as well as the incidence per 1000 person-years, will be presented by eGFR category ($\geq 30 \text{ mL/min/1.73 m}^2$ and $< 45 \text{ mL/min/1.73 m}^2$, $\geq 45 \text{ mL/min/1.73 m}^2$ and $< 60 \text{ mL/min/1.73 m}^2$, $\geq 60 \text{ mL/min/1.73 m}^2$ and $< 90 \text{ mL/min/1.73 m}^2$) and by treatment group.

In addition, for the events in the PT list of adverse events of special interest in the attachment, the numbers and proportions of subjects experiencing said events, and the incidences per 1000 person-years will be presented by treatment group and PT.

Listings

Analysis population(s): Safety Analysis Sets

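### The SAP's incidence formula divides female-only and male-only genital infections by the person-time of both sexes, so both rates come out too low and depend on each arm's sex mix

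*SAP*

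**What the plan says.** SAP 7.7.1 lists the safety endpoints for which an incidence per 1000 person-years is calculated. The list ends with "female mycotic genital infection, male mycotic genital infection, hypoglycemia, malignancy". One formula follows for the whole list, N/P x 1000:

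- The numerator is given only as "N: Safety endpoint sample size", which I read as the number of subjects with the event.
- The denominator is "P: Sum total of the assessment period (in years) of the incidence per 1000 person-years for each subject in the safety analysis population".

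SAP 4.13 sets each subject's period by the same rule for every endpoint, from the first day of treatment to the Week 4 follow-up visit or, without that visit, to the final assessment.

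SAP 7.7.3 makes both genital infection endpoints events of special interest ("female mycotic genital infection, male mycotic genital infection, hypoglycemia, and malignancies"). It names the safety analysis set as the population and says that "the numbers and proportions of subjects experiencing said events, as well as the incidence per 1000 person-years, will be presented for each treatment group". It then asks for the same figures by eGFR category within treatment group.

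SAP 5.2 removes from the randomized subjects only those who were never dosed and those described by "All subjects for which no post-randomization safety data are available". Protocol 3.2 admits either sex, so the safety analysis set contains men and women.

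**The concern.** A man cannot have the female event and a woman cannot have the male event. The stated denominators therefore include person-time, and for the proportions subjects, that can never yield the event. The only purpose of splitting genital infection by sex is to show the risk in each sex, and this denominator defeats it.

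Two things are at stake:

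- **The absolute rates.** A known type of reaction would be understated in the group that experiences it. Section 1 of the protocol already lists vulvovaginal candidiasis among reactions seen in at least 1% of patients.
- **The reading across arms.** SAP 2.3 stratifies randomization by run-in eGFR only. A chance difference in sex mix would therefore move the reported rates apart even where the true risk is the same.

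**Working it through.** The documents state no incidence figure and no sex split for this point, so there is no planned number to reproduce. The check applies the SAP's formula with P over all subjects in an arm, and then with P over the sex at risk only.

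**Inputs**

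- 150 subjects per arm (SAP 2.5).
- Period for a completer on schedule (SAP 4.13): (728 + 28 + 1)/365.25 = 2.0726 years, so 150 x 2.0726 = 310.9 person-years per arm.
- Share of women, f: an assumption, 25% with a range of 20% to 35%, and equal follow-up in both sexes.

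**Step 1: size of the understatement**

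Let r be the true rate in women. The female count per unit of total person-time is r x f, so reported rate = r x f. For men, reported rate = true rate x (1 - f). The two factors add to 1, so both rates are too low whenever both sexes are enrolled. This direction needs no assumption about f.

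| Share of women | Female rate divided by 1/f | Male rate divided by 1/(1 - f) |
|---|---|---|
| 20% | 1/0.20 = 5.0 | 1/0.80 = 1.25 |
| 25% | 1/0.25 = 4.0 | 1/0.75 = 1.33 |
| 35% | 1/0.35 = 2.9 | 1/0.65 = 1.54 |

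**Step 2: illustration with 6 subjects having the event in one arm**

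As planned, 6/310.9 x 1000 = 19.3 per 1000 person-years, whichever sex the endpoint concerns. With sex-specific person-time:

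- 30% women (45 women): 45 x 2.0726 = 93.3 person-years, female rate 6/93.3 x 1000 = 64.3.
- 20% women (30 women): 30 x 2.0726 = 62.2 person-years, female rate 96.5.
- For the male event the rates are 27.6 (105 men) and 24.1 (120 men).

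The proportions behave the same way. Six of 150 is 4.0%, whereas 6 of 45 women is 13.3%.

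**Step 3: effect on the comparison between arms**

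With equal true risk in women, the reported ratio between arms is f1/f2. With f = 25% and 150 per arm, the standard deviation of the chance difference in female share is sqrt(2 x 0.25 x 0.75/150) = 0.05, or 5 percentage points.

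- Equal mix: ratio 1.00, no distortion.
- A gap of 1 standard deviation (27.5% vs 22.5%): 0.275/0.225 = 1.22.
- A gap of 2 standard deviations (30% vs 20%, or 45 vs 30 women of 150): 0.30/0.20 = 1.5.

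For the male event, the 2-standard-deviation gap gives 0.80/0.70 = 1.14. Within an eGFR band there are fewer subjects, so chance imbalance in sex mix is larger than in the whole arm.

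**The case against.** The strongest reply is that the definition of P is a generic template. Read literally it is not even specific to an arm, yet everyone will restrict it to the arm and eGFR band being tabulated. A programmer who makes that inference could equally restrict to women for an endpoint with *female* in its name. On this view the SAP is silent, not wrong. But the restrictions to arm and band are stated: SAP 7.7.3 says the rate "as well as the incidence per 1000 person-years, will be presented for each treatment group" and then by eGFR category. Nothing equivalent is stated for sex, so restricting by sex would be an undocumented departure from an explicit definition.

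Several other points carry weight:

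- The attachment with the preferred-term list is not visible, so a sex condition there cannot be ruled out. SAP 7.7.3 describes it only as a list of terms, and SAP 7.7.1 gives no exception or cross-reference.
- Randomization causes no systematic distortion between arms, and the 1.5 ratio is an edge case: a gap that large, in either direction, has a probability of about 5%.
- SAP 7.7.3 plans no test, confidence interval or ratio for these events, so the comparison is an informal reading of a table.
- Part of the information can be recovered. SAP 7.3 tabulates sex by arm in the safety analysis set, so a reader could rebuild the overall sex-specific proportion and approximate the overall rate. This fails for the eGFR-band tables, because SAP 7.3 gives demographics by band for the FAS only. It also fails for exact rates, because no table gives person-time by sex. The sex subgroups in SAP 7.6.3.8 cover only the eGFR-decline endpoints.

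**Conclusion.** The concern holds. As written, the formula understates both sex-specific genital infection rates, and the proportions in SAP 7.7.3 share the fault. The direction follows from the text alone. The size rests on an assumed sex split and on equal follow-up in the two sexes. If the attachment already restricts the denominators by sex, the main text should say so. If P were pooled over both arms, as its literal wording allows, the rates would be lower still.

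This is a descriptive safety table, and no primary or secondary efficacy result changes. It should still be corrected, because the sponsor has singled these events out as being of special interest and no other planned table gives a sex-specific safety rate.

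**What to change.** Add one sentence to SAP 7.7.1 and repeat it in SAP 7.7.3: for female mycotic genital infection, N, P and the denominator of the proportion include only the female subjects of the safety analysis set in the treatment group concerned and, where applicable, the eGFR category; for male mycotic genital infection, only the male subjects. Show the sex-specific number of subjects in the table headers.

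The cost is that sentence and a subset condition in the table program; no new data are needed. The reported rates will be higher and the numbers per cell smaller, most visibly in the eGFR-band tables.

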7.7.1.1. Adverse Event Incidences

Analysis population(s): Safety analysis set

Analysis parameter(s): Adverse events, adverse reactions, serious adverse events, serious adverse reactions, adverse events leading to study treatment discontinuation, adverse reactions leading to study treatment discontinuation, adverse events leading to death, adverse reactions leading to death

Analysis method:

For events occurring in the adverse event tabulation period, the numbers and proportions of subjects experiencing said events, as well as the incidence per 1000 person-years, will be presented for each treatment group.

Listings

Analysis population(s): Safety Analysis Sets

7.7.1.2. Incidence of Adverse Events by eGFR on the First Day of the Run-in Period (≥ 30 mL/min/1.73 m² and < 45 mL/min/1.73 m², ≥ 45 mL/min/1.73 m² and < 60 mL/min/1.73 m², ≥ 60 mL/min/1.73 m² and < 90 mL/min/1.73 m²)

Analysis population(s): Safety analysis set

Analysis parameter(s): Adverse events, adverse reactions, serious adverse events, serious adverse reactions, adverse events leading to study treatment discontinuation, adverse reactions leading to study treatment discontinuation, adverse events leading to death, adverse reactions leading to death

Analysis method:

For each event occurring in the adverse event tabulation period, the number and proportion of subjects experiencing the event, as well as the incidence per 1000 person-years, will be presented by eGFR category (≥ 30 mL/min/1.73 m² and < 45 mL/min/1.73 m², ≥ 45 mL/min/1.73 m² and < 60 mL/min/1.73 m², ≥ 60 mL/min/1.73 m² and < 90 mL/min/1.73 m²) and by treatment group.

Listings

Analysis population(s): Safety Analysis Sets

7.7.1.3. Individual Adverse Events

Analysis population(s): Safety analysis set

Analysis parameter(s): Adverse events, adverse reactions, serious adverse events, serious adverse reactions, adverse events leading to study treatment discontinuation, adverse reactions leading to study treatment discontinuation, adverse events leading to death, adverse reactions

leading to death

Analysis method:

For each event occurring in the adverse event tabulation period, the number and proportion of subjects experiencing said event will be presented by treatment group and by MedDRA SOC and PT category.

Listings

Analysis population(s): Safety Analysis Sets

7.7.1.4. Adverse Events by Severity

Analysis population(s): Safety analysis set

Analysis parameter(s): Adverse events, adverse reactions

Analysis method:

For each event occurring in the adverse event tabulation period, the number and proportion of subjects experiencing said event will be presented by MedDRA PT and SOC category, by severity, and by treatment group. The severity categories will be “mild,” “moderate,” and “severe.”

Listings

Analysis population(s): Safety Analysis Sets

7.7.1.5. Adverse Events by Causal Relationship to the Investigational Product

Analysis population(s): Safety analysis set

Analysis parameter(s): Adverse events, serious adverse events

Analysis method:

For each event occurring in the adverse event tabulation period, the number and proportion of subjects experiencing said event will be presented by MedDRA PT and SOC category, by causal relationship to the investigational product, and by treatment group. The causal relationship categories will be “reasonable possibility” and “no reasonable possibility” (of there being a causal relationship).

Listings

Analysis population(s): Safety Analysis Sets

7.7.1.6. Adverse Events by Time of Onset

Analysis population(s): Safety analysis set

Analysis parameter(s): Adverse events, adverse reactions

Analysis method:

For each event occurring in the adverse event tabulation period, the number and proportion of subjects experiencing said event will be presented by MedDRA PT and SOC category, by administration duration

(in weeks), and by treatment group.

Treatment Period Duration Categories (in weeks)

< 13, \geq 13 and < 26, \geq 26 and < 52, \geq 52 and < 78, \geq 78

Listings

Analysis population(s): Safety Analysis Sets

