2.1. Objectives

To compare the efficacy and safety of the administration of TA-7284 100 mg once a day for 104 weeks to those of placebo in type 2 diabetes mellitus patients with Stage 3 diabetic nephropathy (overt nephropathy).

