- k) Serious adverse events will be investigated from informed consent acquisition up until Week 4 of the follow-up observation period. Other adverse events will be investigated from after the start of the administration of the treatment period investigational product up until Day 14 of the follow-up observation period.
- l) The instructions on blood glucose self-measurement (SMBG) and on completing the hypoglycemia symptoms survey form will be given on the first day of the run-in period. Blood glucose self-measurements will be performed whenever possible when the patient experiences symptoms of hypoglycemia.

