7.7.2. Hypoglycemia

Analysis population(s): Safety analysis set

Analysis parameter(s): Hypoglycemia

Analysis method:

The number and proportion of subjects experiencing hypoglycemia (blood glucose decreased, hypoglycemic coma, hypoglycemic unconsciousness, hypoglycemic seizure, hypoglycemia) in the adverse event tabulation period, and the incidence per 1000 person-years, will be presented by treatment group. The number and proportion of subjects and the incidence per 1000 person-years will be presented by hypoglycemia category and treatment group. The number and proportion of subjects experiencing hypoglycemia will also be presented by treatment period and treatment group. For the attached hypoglycemia PT list, the number and proportion of subjects experiencing each event, as well as the incidence per 1000 person-years, will be presented by treatment group and by SOC and PT (blood glucose decreased, hypoglycemic coma, hypoglycemic unconsciousness, hypoglycemic seizure, hypoglycemia).

Hypoglycemia Categories

Severe hypoglycemia, documented symptomatic hypoglycemia, asymptomatic hypoglycemia, probable symptomatic hypoglycemia, relative hypoglycemia

Treatment Period Categories (in weeks)

< 13, \geq 13 and < 26, \geq 26 and < 52, \geq 52 and < 78, \geq 78

Listings

Analysis population(s): Safety Analysis Sets

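### The onset-timing tables for adverse events and hypoglycemia give only proportions over intervals of unequal length, so a steady risk of an uncommon event appears to rise about 1.8-2.0 fold after Week 26

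*SAP*

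**What the plan says.** SAP 7.7.1.6 covers adverse events and adverse reactions by time of onset. Its statistic is "the number and proportion of subjects experiencing said event will be presented by MedDRA PT and SOC category, by administration duration", split by arm. The cut-points are Weeks 13, 26, 52 and 78, and the last category is open-ended. The only population named is in the line "Analysis population(s): Safety analysis set".

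SAP 7.7.2 uses the same cut-points for hypoglycemia: "The number and proportion of subjects experiencing hypoglycemia will also be presented by treatment period and treatment group". The other tabulations in that section (overall, by hypoglycemia category and by preferred term) all carry a rate per 1000 person-years. The by-period sentence does not.

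Rates also appear in SAP 7.7.1.1 ("the numbers and proportions of subjects experiencing said events, as well as the incidence per 1000 person-years, will be presented for each treatment group"), 7.7.1.2 and 7.7.3, always over the whole study. SAP 7.7.1 defines the denominator of those rates as one total: "P: Sum total of the assessment period (in years) of the incidence per 1000 person-years for each subject in the safety analysis population". SAP 4.13 gives each subject's contribution as a single span from the first day of treatment. Neither section splits person-time by interval.

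**The concern.** These two tables exist to show when events occur during 104 weeks of treatment. A proportion of subjects depends on how long the interval is as well as on the risk. The third interval is twice as long as the second, so a reader who scans the row sees a step at Week 26 even when the risk has not changed.

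Discontinuation acts in the opposite direction. Under protocol 12.2, follow-up starts once the treatment period is discontinued, and SAP 2.4.1 collects non-serious events only "up until Day 14 of the follow-up observation period". A subject who stops at Week 30 therefore cannot contribute a non-serious event after Week 78. If that subject stays in the denominator, the later proportions are pulled down.

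At stake is the reading of early versus late onset, row by row. A steady risk may be described as late-emerging, or a risk that falls over time may look steady.

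**Working it through.** The documents give no figure for these tables, so there is nothing to reproduce. The check asks what the tables would show if the risk were constant.

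**Inputs from the documents**
- Cut-points at Weeks 13, 26, 52 and 78 (SAP 7.7.1.6 and 7.7.2).
- Treatment of 104 weeks: "TA-7284 100 mg once a day for 104 weeks" (SAP 2.1).
- Non-serious events collected to Day 14 of follow-up (SAP 2.4.1), so the last interval runs to about Week 106 and lasts 106 - 78 = 28 weeks. It is 26 weeks if cut at Week 104, and 30 for serious events, which are collected to follow-up Week 4.
- Planned size of 150 per arm (SAP 2.5).

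**Assumptions, not in the documents**
- Constant event rate between 20 and 2000 per 1000 person-years.
- Exponential discontinuation of 0% to 30% by Week 104.
- A subject may be counted in more than one interval, and one year is 52.18 weeks.

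**Formula.** With event hazard h, discontinuation hazard d, interval start a and width w (in years), and all safety-set subjects as denominator:

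proportion = exp(-d·a) × h/(h+d) × (1 - exp(-(h+d)·w))

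**Step 1. Width alone.** With h = 0.1 per year and d = 0, 13 weeks gives 1 - exp(-0.1 × 0.249) = 2.46% and 26 weeks gives 1 - exp(-0.1 × 0.498) = 4.86%. The five intervals show 2.46, 2.46, 4.86, 4.86 and 5.22%. The ratio of Weeks 26-52 to Weeks 13-26 is 1.98.

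**Step 2. Other rates and discontinuation.** Ratio of Weeks 26-52 to Weeks 13-26:

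| Rate per 1000 person-years | No discontinuation | 20% by Week 104 | 30% by Week 104 |
|---|---|---|---|
| 20 | 2.00 | 1.91 | 1.87 |
| 100 | 1.98 | 1.89 | 1.85 |
| 200 | 1.95 | 1.87 | 1.83 |
| 500 | 1.88 | 1.81 | 1.76 |
| 1000 | 1.78 | 1.71 | 1.67 |
| 2000 | 1.61 | 1.55 | 1.51 |

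If each subject is counted only at the first event in the whole study, the ratio without discontinuation is 1.93 at 100, 1.66 at 500, 1.39 at 1000 and 0.98 at 2000. For very common events counted that way the step disappears.

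**Step 3. At-risk denominator without person-time.** At 100 per 1000 person-years with 20% discontinuation, dividing by those still observed at the start of each interval gives a ratio of 1.95. The number at risk alone does not remove the width effect.

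**Step 4. Comparison of arms.** Width is the same in both arms. To see what unequal discontinuation could do, take h = 0.2 per year in both arms, with a discontinuation hazard of 0.05 per year in one and 0.15 or 0.20 in the other (9% against 26% or 33% gone by Week 104). In the last interval the fixed-denominator proportions are 9.3% against 7.8% or 7.2%, which is 16% or 23% lower. In subjects, that is 14.0 against 11.7 or 10.7 of 150. The larger gap is 2.2 percentage points, with a standard error of about 3.2 points.

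**Step 5. Which rate works.** Dividing subjects with an event by the full person-time in the interval is still affected by width. With h = 1 per year and no discontinuation it gives (1 - exp(-0.249))/0.249 = 885 per 1000 person-years over 13 weeks and (1 - exp(-0.498))/0.498 = 788 over 26 weeks, a false decline. If person-time stops at the first event in the interval, the expected person-time per subject is (1 - exp(-h·w))/h and the rate is h, or 1000 per 1000 person-years, in both. Counting all events over full person-time also gives a flat rate. At h = 0.1 with 20% discontinuation and 150 subjects, person-years are 36.9, 35.8, 68.8, 65.0 and 66.1, expected events are 3.69, 3.58, 6.88, 6.50 and 6.61, and the rate is 100 throughout.

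**The case against.** **Numbers remaining are largely available elsewhere.** SAP 7.5.1 tabulates treatment duration by arm at the same cut-points, so the numbers still on treatment at Weeks 13, 26, 52 and 78 follow by subtraction. SAP 7.2.2 adds discontinuations and their reasons. This stands in part. That table uses the FAS and counts treatment rather than adverse-event observation, and it gives no person-time by interval.

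**The tables follow the SAP's own convention.** The related breakdowns by term, severity and causality (7.7.1.3 to 7.7.1.5) also give only numbers and proportions, and protocol 13.3.3 promises no more. That is true, but those tables do not compare intervals of different length.

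**The unequal widths are printed as category labels.** They are, and a careful reader can allow for them. Whole-study rates are planned as well, but they cannot show timing.

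**Stronger readings that the documents do not support.** A reader might infer that subjects who have left stay in every denominator. The SAP names a population and does not state the denominator. A reader might also infer that the comparison of arms is biased. Width cannot do that, and the 16-23% gap in step 4 needs a three- to four-fold difference in discontinuation hazard, for which the documents give no evidence. Finally, the wording on administration duration could mean grouping subjects by total exposure, but the section title points to time of onset.

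**Conclusion.** The point holds as a limitation of two descriptive tables. Under a constant risk, the proportion in Weeks 26-52 is about 1.8-2.0 times that in Weeks 13-26 for events up to about 200 per 1000 person-years, with up to 30% discontinuation. The ratio falls to about 1.5-1.6 at 2000 per 1000 person-years, and the step can vanish for very common events counted at first onset only. With a fixed safety-set denominator, discontinuation partly offsets the width effect, so a flat doubling in every row would overstate it.

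The interval widths are the SAP's own. The event rates, the discontinuation and the constant hazard are assumptions. Whole-study rates are planned for the main categories, no test or decision depends on the onset tables, and the primary analysis is untouched. Priority is minor.

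**What to change.** In SAP 7.7.1.6 and the by-period hypoglycemia table of 7.7.2:

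- State the denominator, and show by arm the number of safety-set subjects still under adverse-event observation at the start of each interval.
- Add an interval-specific rate per 1000 person-years. Either divide subjects with an event in the interval by person-time stopped at each subject's first such event in that interval, or divide all events by the full person-time in the interval. Say which is used.
- State where the last interval ends.

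Onset dates and the dates that bound each subject's observation are already collected, so no new data are needed. The cost is a few lines of SAP text, a little programming and slightly longer tables.
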